6. DATA COLLECTION, MANAGEMENT, AND SECURITY

6.1 Data Collection

Data will be collected on enrolled children at baseline (time of enrollment), and follow-up weeks 1-12. Written informed consent will be collected on paper and the study officer administering treatment will record treatment administration on Taimaka's internal ap. All other data will also be collected electronically on mobile devices using ODK mobile application.

Data from the study participants is stored in the same database as data from all of Taimaka's patients. Taimaka will share the entire database with UCSF, and the UCSF study team will write a carefully-worded statistical programming script to only select records and data of the study participants.

6.2 Data Management and Security

Electronic data will be uploaded daily to a secure, password-protected, cloud-based server hosted by Taimaka. All devices used for data collection will be password-protected, as will the mobile application itself. Paper forms will be stored in locked cabinets accessible only by specific study team members at each enrollment site.

Study indicators and PII will be collected electronically and stored securely in Taimaka's password-protected, cloud-based server. Study data will only be accessible by study team members and investigators in order to protect confidentiality.

6.3 Data Quality and Monitoring

All study team members collecting data will undergo an initial training to learn how to use the mobile devices as well as best practices for data collection. Data collection will be monitored on a weekly basis by the study team. Concerns over data quality and completeness will be relayed to the local study team by email, and refresher trainings and/or additional supervision of data collection by local investigators will be planned as needed. The study team will send quarterly progress reports to the DSMC, including aggregate data on enrollment and follow-up status, weight gain, nutritional recovery, and adverse events.

7. PROTECTION OF HUMAN SUBJECTS

Before any study procedures are implemented, the study team will obtain Institutional Review Board (IRB) approval from committees at UCSF and Nigeria. In addition, local study team members will approach each potential enrollment site to describe the study and obtain their consent to participate as a study site. At the individual level, study personnel will obtain written informed consent from at least one parent or guardian for all study activities. Any guardians who are illiterate will be provided an impartial witness to explain the consent form at the time of enrollment. If, at any time, a parent or guardian elects to withdraw a child from the study, they will be free to do so. Individuals who withdraw will be offered the same standard of care outside the study.

7.1 Institutional Review Board Approval

University of California, San Francisco (UCSF) Committee on Human Research

UCSF's Committee on Human Research will annually review the study protocol for ethical approval.

Gombe State Ministry of Health

The study protocol will be reviewed and granted ethical approval by these 2 committees in Nigeria before any study activities begin.

7.2 Informed Consent

Study personnel fluent in relevant local languages will approach parents or guardians of eligible children at the enrollment site. In a private setting, the study team member will explain the objectives, risks, and benefits of the study as well as detailed information about what study participation entails for the child and the parent or guardian. The study team member will clarify that participation in the study is voluntary, that participation may be stopped at any time, and that all collected data will be kept confidential and securely stored. The study team member will ensure comprehension by inviting the parent or guardian to ask questions and will provide time for the parent or guardian to consider participation. Any guardians who are illiterate will be provided with an impartial witness to explain the consent form. When providing consent, both the study team member and the parent or guardian will sign two copies of the consent document. One copy will be given to the parent or guardian and the other will be kept for study reference.

8. DATA AND SAFETY MONITORING COMMITTEE

The Data and Safety Monitoring Committee (DSMC) will consist of independent experts in biostatistics, epidemiology, child health and nutrition, and/or global public health.

The DSMC will be empaneled prior to the beginning of the study. The committee will meet once prior to the start of the study and at the study's conclusion. All study protocols will be subject to review and approval by Institutional Review Boards at UCSF and Nigeria, and by the DSMC.

The DSMC will be notified in real time of serious adverse events (SAEs). They will notify the study team if they would like to receive information about SAEs in a different manner. Committee members will monitor any severe or unexpected trend that threatens the safety of study participants. The DSMC will be authorized to end the study if they deem necessary (e.g., safety, feasibility).

The study team will send the following reports to the DSMC:

- A report at 1 month post-enrollment
- A report when 50% of the enrollment target has been reached (at 300 participants enrolled)
- A study close-out report at the end of the study

A study closeout meeting will be scheduled at the end of the study unless deemed unnecessary.

9. STATISTICAL METHODS

9.1 Sample Size and Power

Specific Aim 1 We assume that inclusion of 600 children (300 randomized to each arm) will provide 80% power to detect a 15% increase in weight gain (g/kg/day) in children receiving azithromycin compared to children receiving amoxicillin at an alpha of 0.05. Assumptions for this calculation were based on the pattern of weight gain reported in a trial of routine amoxicillin for uncomplicated SAM in Burkina Faso comparing children receiving azithromycin to amoxicillin over time.¹¹ We assumed an average weight gain of 2.6 g/kg/day over 8 weeks in the amoxicillin arm, with a standard deviation of 1.7 g/kg/day, and loss to follow-up of 10%. A 16% increase corresponds to a mean difference in weight gain of 0.4 g/kg/day, or an average weight gain of 3.0 g/kg/day in the azithromycin arm.

This calculation was performed in Stata using the following command:

```
power twomeans 2.6, sd(1.7) alpha(0.05) power(0.8) n(540)
```

Specific Aim 2. Inclusion of 600 children (300 randomized to each arm) will provide 80% power to detect a 12 percentage point difference in the proportion of children achieving nutritional recovery in the azithromycin arm compared to the amoxicillin arm. Assumptions for this calculation were based on nutritional recovery reported in the amoxicillin arm of a trial of routine amoxicillin compared to azithromycin for uncomplicated SAM in Burkina Faso.¹¹ We assumed that 36% of children in the oral amoxicillin arm would achieve nutritional recovery and a loss to follow-up of 10%.

This calculation was performed in Stata using the following command:

```
power twoproportions 0.36, alpha(0.05) power(0.8) n(540)
```

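### The 80% power claimed for a 15% increase in weight gain is about 76% with the 540 children the plan expects to analyse; 15% holds only if nobody is lost

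*Combined protocol and SAP*

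**What the plan says.** Section 9.1, Specific Aim 1, bases the power statement on 600 enrolled children, split equally between the arms, and claims "80% power to detect a 15% increase in weight gain (g/kg/day) in children receiving azithromycin".

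The inputs follow in the same paragraph. The control mean is 2.6 g/kg/day. The remaining two assumptions, the spread and the attrition (the latter in percent), are stated as "with a standard deviation of 1.7 g/kg/day, and loss to follow-up of 10".

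The effect is then described a second time, with a different percentage: "A 16% increase corresponds to a mean difference in weight gain of 0.4 g/kg/day". The implied mean under azithromycin is put at 3.0.

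The printed Stata command is "power twomeans 2.6, sd(1.7) alpha(0.05) power(0.8) n(540"). It fixes the number analysed and the power, gives no second mean, and so solves for the detectable difference.

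**The concern.** The paragraph gives two percentages, 15% and 16%, for what should be one target effect. With one mean, one SD, one alpha and one analysed number, only one difference can have exactly 80% power. The opening sentence carries the smaller, more favourable figure, while the command beneath it already allows for 10% loss.

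This is the power statement for the primary outcome, and the opening sentence is the one most likely to be carried into reports. If the trial finds no difference, it would be described as having had 80% power for a 15% gain when the planned analysis set does not provide that.

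**Working it through.** **Inputs**

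- Control mean 2.6 g/kg/day, SD 1.7, alpha 0.05, loss 10%: Section 9.1.
- Analysed number: 600 × 0.9 = 540, or 270 per arm, as in the command.
- Two-sided test: the command requests no one-sided option, and Section 9.2 reports 95% confidence intervals at the 0.05 level.
- Model: Section 9.2 specifies a linear regression with only a treatment indicator. This is equivalent to a two-sample t-test, so no precision is gained from covariates.
- Missing data: Section 9.2 analyses complete cases when no more than 10% are missing, so 540 is the analysed number at the planned loss.

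**Step 1: reproduce the command.** The standard error of the difference is

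SE = SD × √(2/n) = 1.7 × √(2/270) = 0.1463.

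The detectable difference at 80% power (normal approximation) is

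(1.960 + 0.842) × 0.1463 = 0.410 g/kg/day.

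The noncentral t gives 0.411. As a percentage, 0.411/2.6 = 15.8%, and the implied azithromycin mean is 3.01. Rounded, these are the paragraph's 16%, 0.4 and 3.0.

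**Step 2: test the 15% claim.** 15% of 2.6 is 0.39. Then 0.39/0.1463 = 2.666, and

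power ≈ Φ(2.666 − 1.960) = Φ(0.706) = 76.0%.

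The noncentral t gives 75.8%.

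**Step 3: power for each way of reading the effect.**

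| Difference (g/kg/day) | Increase over 2.6 | Power, 540 analysed (normal / t) | Power, 600 analysed (normal / t) |
|---|---|---|---|
| 0.39 | 15.0% | 76.0% / 75.8% | 80.2% / 80.1% |
| 0.40 | 15.4% | 78.1% / 77.9% | 82.2% / 82.0% |
| 0.41 | 15.8% | 80.0% / 79.9% | 84.0% / 83.9% |
| 0.416 | 16.0% | 81.1% / 81.0% | 85.0% / 84.9% |

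With all 600 analysed, the detectable difference at 80% power is 0.389 g/kg/day, or 15.0%. The opening sentence therefore matches a calculation without loss.

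**Step 4: number needed for 15%.** Normal approximation, per arm:

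n = 2 × (1.960 + 0.842)² × 1.7² / 0.39² ≈ 298.3, so 299.

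The noncentral t gives 299.2 per arm, or about 599 in total. Allowing for 10% loss, 598.5/0.9 = 665 enrolled. Rounding up to 300 per arm gives 600/0.9 ≈ 667.

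**Step 5: could a one-sided test explain it?** No. A one-sided 0.05 test with 540 analysed gives 84.6% for 0.39, which is not 80% either.

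**The case against.** The strongest reply is that the calculation is sound and only one number in the prose has slipped. The command allows for dropout, and 16%, 0.4 and 3.0 are its output correctly rounded. That stands: 16% and 0.4 should be read as one effect reported to limited precision, and the only real conflict is between 15% and the rest.

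It is also fair that power does not determine what a null result excludes. The confidence interval does that, and the plan reports one. The label of 15% changes no estimate, interval or decision rule.

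The gap is also small beside the uncertainty in the inputs. The SD is taken from a study whose title in the reference list calls it a pilot. An SD of about 1.61, some 5% lower, would give 80% power for 15% with 540 analysed, and a rise of similar size would cost about as much. Finally, the plan gives no reason for 15% as a target, so the figure of 665 should not be read as evidence that the trial is under-enrolled.

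These points limit the consequence but do not make the opening sentence true. Rounding turns 15.8% into 16%, not 15%, and nothing elsewhere in the plan recovers the missing power.

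**Conclusion.** The concern holds. On the plan's own inputs, power for a 15% increase is about 76%, not 80%, and the difference detectable with 80% power is 0.41 g/kg/day (15.8%). A 15% increase has 80% power only if about 599 to 600 children are analysed, which conflicts with the 10% loss assumed in the same paragraph.

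The shortfall is about 4 percentage points of power, or 0.02 g/kg/day in detectable difference. The sample size of 600 remains adequate for an effect of about 16%. This rests on a two-sided test at 0.05, equal arms, an SD of 1.7 in both arms, the unadjusted model and exactly 10% loss.

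**What to change.** Restate Section 9.1, Specific Aim 1, with one effect size throughout, for example:

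> With 600 children enrolled and 540 analysed after 10% loss, the trial has 80% power (two-sided 0.05, SD 1.7) for a difference of 0.41 g/kg/day (2.6 vs 3.01, an increase of about 16%). Power for a 15% increase (0.39 g/kg/day) is about 76%.

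The cost is one corrected paragraph and a slightly less favourable headline figure. Neither enrolment nor the analysis changes. If the sponsor does intend 15% as the target, it should say so and either accept about 76% power or plan for about 665 to 667 enrolled.

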9.2 Statistical Analysis

Baseline characteristics. Characteristics of the study population collected at baseline will be summarized using frequencies and percentages for categorical variables and means and standard deviations or medians and inter-quartile ranges for continuous variables. Baseline characteristics will be compared by treatment arm using Fisher's exact test for categorical variables and t-tests or Wilcoxon rank-sum tests for continuous variables.

Specific Aim 1. The primary analysis will compare weight gain velocity (g/kg/day) between groups over the 8-week follow-up period. We will estimate mean differences and 95% confidence intervals for the difference using a linear regression model with an indicator for study group.

$$E[Y | X = x] = \beta_0 + \beta_1 X + e$$

Where:

- **Y = weight gain velocity from enrollment to 8 weeks**
- X = binary indicator for treatment group ($X=1$ for azithromycin, $X=0$ for a short course of oral amoxicillin)

- β_1 = difference in weight gain velocity between the azithromycin group compared to a short course of oral amoxicillin group
- $e \sim N(0, \sigma^2)$

Sensitivity analyses will include similar linear models to assess period-specific weight gain by group from week 0-1, 1-2, 2-4, and 4-8.

Specific Aim 2. The primary analysis will compare nutritional recovery by 8 weeks from baseline by arm. We will use log-binomial regression for this analysis to estimate the risk ratio. We will use the following model:

$$\log[P(Y = 1|X_1 = x_1)] = \beta_0 + \beta_1 X_1 + e$$

Where:

- **Y = binary indicator for nutritional recovery by 8 weeks ($Y=1$ for recovered, $Y=0$ for not recovered)**
- X = binary indicator for treatment arm ($X=1$ for azithromycin, $X=0$ for a short course of oral amoxicillin)
- e^{β_1} = relative risk of nutritional recovery in azithromycin arm compared to a short course of oral amoxicillin arm
- $e \sim N(0, \sigma^2)$

If the log-binomial model fails to converge, we will use a modified Poisson model with robust standard errors as an alternative.

Secondary outcomes.

Time to event outcomes (time to recovery and time to mortality) will be assessed visually using Kaplan-Meier curves and compared by arm using the log-rank test.

Binary outcomes will be analyzed using modified Poisson regression for rare outcomes (e.g. mortality) or log-binomial regression for common outcomes (e.g. malaria), using models similar to the one described above for Specific Aim 2.

Anthropometric assessments will be analyzed using linear models as described for Specific Aim 1, with correction for baseline values. For anthropometric assessments, z-scores will be calculated based on the 2006 WHO Child Growth Standards. Anthropometric z-scores will be analyzed as continuous variables and secondary analyses will explore categorization.

All analyses will be intention-to-treat. A significance level of 0.05 for inference and 95% confidence intervals will be reported for all effect estimates. All analyses will be conducted using R (R Foundation for Statistical Computing, Vienna, Austria). For all models, model diagnostics will be conducted to assess appropriate fit.

Missing data.

If $\leq 10\%$ of enrolled children is missing outcome data, complete case analyses will be conducted. If $> 10\%$ of enrolled children are missing outcome data, inverse probability weighting will be used to weight complete cases by the inverse of an estimate of the probability of an outcome being observed as a sensitivity analysis. Weights will be constructed with the following

baseline characteristics chosen as factors likely to predict follow-up: SES, distance from health center, WHZ, and MUAC.

REFERENCES

2. Page AL, de Rekeneire N, Sayadi S, et al. Infections in children admitted with complicated severe acute malnutrition in Niger. *PLoS One*. 2013;8(7):e68699. doi:10.1371/journal.pone.0068699

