2.2 Recruitment and Eligibility Criteria

Recruitment

Taimaka-employed community mobilizers (CMs) screen children for SAM at least once a month in the villages within the catchment areas of the program PHCs. If they are screened positive for moderate acute malnutrition (MAM) or SAM, they are referred to an OTP center. CMs screen for MAM and SAM using a tape to measure mid-upper arm circumference (MUAC).

Each participating OTP center has nutrition staff (henceforth known as health agents) trained to enter data and conduct anthropometric measurements. All data is collected electronically on an ODK custom platform. The health agents at the OTP centers are trained regularly on malnutrition guidelines, data collection and anthropometric measurements

All children presenting to the OTP centers for malnutrition will be screened, and eligibility for enrollment in the trial will be determined by health agents trained for the study.

Eligibility criteria for enrollment sites

For Phase 1, the 3 Taimaka-run OTP centers in Gombe state that will be eligible for enrollment are located within 1) General Hospital Deba, 2) General Hospital Bajoga, and 3) General Hospital Billiri.

For Phase 2, the Taimaka-run OTP centers in Gombe state will be located in PHCs in wards in these local government areas (LGAs): Deba, Billiri, and Funakaye (Bajoga is a town within the Funakaye LGA).

Eligibility criteria for individuals

Eligible individuals are children aged 6-59 months with SAM who present to an eligible OTP center during the study period and meet all of the following criteria:

Inclusion criteria (all must be met):

- Age 6-59 months
- Weight-for-height z-score (WHZ) < -3 SD or mid-upper arm circumference (MUAC) < 115 mm
- Either (a) no oedema or (b) Nutritional edema Grade I and II
- Primary residence within catchment area of enrollment site
- Available for full 8-week study
- Sufficient appetite according to a feeding test with ready-to-use therapeutic food (RUTF)
- Appropriate written informed consent from at least one parent or guardian

Exclusion criteria (any excludes):

- Age < 6 months or > 59 months
- WHZ \geq -3 SD or MUAC \geq 115 mm
- Primary residence outside catchment area of enrollment site
- Not available for full 8-week study
- Presence of nutritional edema Grade III
- Admission to a nutritional program for the treatment of SAM in the 2 preceding weeks
- Antibiotic use in past 7 days
- Clinical complications requiring antibiotic treatment

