2.3 Randomization and Masking

Children meeting inclusion criteria will be enrolled by a local health agent after consent from guardian is obtained. At enrollment, children will be assigned a study identification number. Enrolled children will then undergo a baseline assessment. The baseline assessment includes data collection on demographics and socioeconomic status as well as anthropometric assessments. After completion of the baseline assessment, children will be randomized to receive either (1) a single dose of directly observed oral azithromycin plus a 5-day course of placebo or (2) a 5-day course of oral amoxicillin.

The randomization sequence will be generated by the UCSF investigators using R (R Foundation for Statistical Programming, Vienna, Austria). Children will be randomized in a 1:1

fashion to a single dose of azithromycin with short course of placebo or a short course of oral amoxicillin. The randomization sequence will be linked to the study identification numbers and kept separately so outcomes assessors are not aware of the treatment allocation. When a child has been enrolled and has completed the baseline assessments, a different health agent will determine the allocation and will administer study medication indicated as described in Section 4.

To keep the allocation concealed, only the study nurse administering treatment will have access to the randomization allocations. The study nurse will treat the child in a private room without the outcome assessor present. For each enrolled child, the treatment administered will be recorded on the mobile data collection app not accessible by the outcome assessor.

Given the nature of the intervention, the personnel administering treatment will not be masked to treatment assignment. Participants will be masked to treatment assignment, as parents of the children given azithromycin will receive a placebo syrup to give their child. Outcome assessors will be masked to treatment assignment; this will be accomplished by assigning one health agent to administer treatment and a separate masked health agent to perform outcome assessments, including anthropometry, and vital status updates.

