3.2 Anthropometry

Anthropometric assessments (height or length, weight, and MUAC) will be recorded by health agents at baseline, weekly until recovery, week 8 and week 12.

Supplies

- Mobile data collection device & accessories
- Height and length tapes
- Digital scale
- MUAC strips
- Chucks and alcohol swabs
- Pens and sharpie markers
- Trash bags
- Extra set of AA batteries (6)

[figure not shown]
Anthropometry Team

Two health agents will conduct anthropometry: 1) examiner and 2) recorder. The examiner will conduct the anthropometric assessments, and the recorder will enter data into the mobile application.

Measuring Length (National operational guidelines for CMAM Nigeria)

How to measure LENGTH (when lying down) If the child is less than 87cm, he/she should be measured lying down.

1. One person holds the child's head, making sure the child's head is touching the back of the board. The child's eyes should be looking straight up.
2. The other person holds down the child's knees, pressing the sliding wood piece against the child's heels and soles of the feet.
3. Align the child with the board
4. Child's arms should be lying alongside his/her body, and if necessary, the mother can hold the arms down
5. The person holding the feet reads the measurement.

[figure not shown]

Measuring Height (National operational guidelines for CMAM Nigeria)

How to measure HEIGHT (when standing) If the child is more than 87cm, he/she should be measured standing.

1. Place the child's feet flat and together in the centre of and against the back and base of the wall.

2. One person places their right hand just above the child's ankles on the shins, left hand on the child's knees and push against the wall. Make sure the child's legs are straight and the heels and calves are against the wall
3. Tell the child to look straight ahead making sure the child's line of sight is level with the ground.
4. The second person should place their open left hand under the child's chin. Do not cover the child's mouth or ears. Make sure the shoulders are level, the hands are at the child's side, and the head, shoulder blades, and buttocks are against the wall.
5. When the child's position is correct, person holding the legs reads (at eye level) and call out the measurement to the nearest 0.1 cm.

Measuring Weight

Tempered glass digital standing scales will be used to weigh infants and children to the nearest 0.1 kg.

For infants and children who cannot stand:

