3.5 Assess for bilateral pitting oedema

Assessing for oedema will be done at enrollment to ensure eligibility and will also be assess at each weekly visits

1. While child is sitting, grasp both feet in your hands. Apply firm thumb pressure to the tops of both feet for three full seconds (count 101, 102, 103). Remove the thumbs.
2. If the depression from your thumbs remains on both feet, then the patient has bilateral pitting oedema. It may be easier to feel this depression than to see it.
3. If tops of feet are edematous, repeat the process on the shins and hands.
4. If the shins / hands are edematous, observe for oedema around the eyes.

Oedema is nutritionally significant if it is present on both feet. However, bilateral pitting also be caused by medical conditions such as nephritic syndrome. Medical causes should be first ruled out before the diagnosis of nutritional Oedema is made.

Grades of oedema

Grade of oedema	Observation
Absent	Absent, no oedema
Grade +	Mild: both feet / ankles
Grade ++	Moderate: both feet + lower legs
Grade +++	Severe: generalized oedema including both feet, legs, hands, arms and face/head

Grade +

Grade ++

Grade +++

Only children with grade + and grade ++ will be eligible to participate in the study.

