Any child with grade 3 (++) oedema should be referred to the ITP. Additionally, OTP staff should request a urinalysis test for children with grade 1 (+) or grade 2 (++) oedema. This test will be carried out by the lab assistant. The results of this test will be used to identify non-nutritional causes of oedema, such as kidney problems. A protein result of >2 indicates that the child may have non-nutrition oedema. Children with non-nutritional oedema should be advised to visit a hospital to check for other health problems. These steps are outlined in the table below.

Additionally, because nutritional oedema begins in the feet and moves upward, caregivers should also be asked where the oedema began. If it did not begin in the feet, advise the caregiver to visit a hospital.

SAM patients should be referred to the ITP in the event of:

Criterion	Time after admission into OTP
Severe complications (defined in next lecture)	At any visit
Failure to gain any weight (non-edematous children)	21 days
Weight loss since admission to program (non-edematous children)	14 days
Failure to start to lose edema	14 days

Edema still present	21 days
Weight loss of 5% of body weight (non-edematous children)	At any visit
Failure of appetite test	At any visit
Failure to start to gain weight satisfactorily after loss of edema (kwashiorkor) or from day 14 (marasmus) onwards. Satisfactory is determined as 'at least 5 g/kg of body weight per day.'	At any visit
Failure to gain weight (rule out RUTF sharing, selling, other noncompliance, etc.) (non-oedematous children)	Any 14 day interval
Weight loss for two successive visits	At any visit
No MUAC gain for two consecutive weeks	At any visit

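### The primary weight-gain model uses no baseline covariates, though useful ones are already collected, and no analysis of weight gain separates children with oedema

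*Combined protocol and SAP*

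**What the plan says.** Section 9.2 (Specific Aim 1) defines the primary analysis: "We will estimate mean differences and 95% confidence intervals for the difference using a linear regression model with an indicator for study group". The equation has an intercept and an arm term only. The one further set of Aim 1 analyses is by period: "Sensitivity analyses will include similar linear models to assess period-specific weight gain by group from week 0-1, 1-2, 2-4, and 4-8". These pool children with and without oedema.

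Baseline correction does appear in section 9.2, but under secondary outcomes: "Anthropometric assessments will be analyzed using linear models as described for Specific Aim 1, with correction for baseline values".

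The candidate covariates exist before allocation. Section 2.3: "After completion of the baseline assessment, children will be randomized to receive either" one of the two regimens. Section 3.2: "Anthropometric assessments (height or length, weight, and MUAC) will be recorded by health agents at baseline, weekly until recovery, week 8 and week 12". Section 3.5: "Assessing for oedema will be done at enrollment to ensure eligibility and will also be assess at each weekly visits". Age is an eligibility item in section 2.2.

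Section 2.2 admits children with mild or moderate oedema: "Either (a) no oedema or (b) Nutritional edema Grade I and II". In the referral table of section 5.2, four rows on weight are restricted to children without oedema, and another judges gain only once oedema has gone.

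**The concern.** Two things are at stake.

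The first is precision. Baseline variables that predict weight gain reduce residual variance and so narrow the interval for the arm difference. They also absorb chance imbalance, as far as linear terms fit. The plan uses baseline values for secondary anthropometry, and lists WHZ and MUAC among the predictors for its missing-data weights, but gives the primary outcome none. It will test baseline characteristics by arm without saying what follows from an imbalance.

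The second is interpretation. Gain is measured from enrolment weight. When oedema clears, the lost fluid counts as negative gain, although it is a sign of recovery. Adjusting for oedema does not change what the outcome measures in such a child. Only an analysis without these children would show whether the result depends on them. The period models help in part: weeks 4-8 should largely miss early fluid loss, while weeks 0-1 are the most exposed to it.

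**Working it through.** **Inputs from section 9.1.** 600 enrolled and 10% loss give N = 540 (270 per arm); SD 1.7 g/kg/day; control mean 2.6; difference 0.40; alpha 0.05, taken as two-sided. The section calls the same effect both 15% and 16%; I use its 0.40.

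**The plan's own figure.** SE = 1.7 × √(2/270) = 0.1463. By the noncentral t with 538 df, 80% power is reached at a difference of 0.411, which is 15.8% of 2.6 and rounds to the stated 0.4 and 16%. At exactly 0.40, power is 77.9% and the 95% CI half-width is 0.287.

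**Adjusted model.** With k covariate terms that explain a share R² of the variance:

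SE = 1.7 × √[(1 − R²) × (1 + k/(540 − k − 2)) × 2/270], df = 538 − k.

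Oedema (two terms), WHZ, MUAC and age give k = 5. The cost factor is 1 + 5/533 = 1.0094. Adding local government area gives k = 7 and 1 + 7/531 = 1.0132. R² is not in the documents, so a range is assumed.

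| R² | Power, k = 5 | Half-width, k = 5 | Power, k = 7 |
|---|---|---|---|
| 0 | 77.5% | 0.289 | 77.4% |
| 0.05 | 79.6% | 0.281 | 79.4% |
| 0.10 | 81.7% | 0.274 | 81.5% |
| 0.20 | 85.9% | 0.258 | 85.8% |

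Break-even for k = 5 is R² = 1 − 1/1.0094 = 0.009; for k = 7 it is 0.013. The equivalent unadjusted sample size is 540/[1.0094 × (1 − R²)]: 563 at R² 0.05 (23 more children) and 594 at 0.10 (54 more).

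**Oedema alone.** Assume that fluid is 2-8% of enrolment weight, and that children with oedema otherwise gain like the rest. Clearing it lowers 56-day gain by d = 1000 × fluid/56, that is 20/56 = 0.36 to 80/56 = 1.43 g/kg/day. At prevalence p, R² = p(1 − p)d²/1.7². Power is for k = 2.

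| Prevalence | Fluid | R² | Power |
|---|---|---|---|
| 5% | 2% | 0.002 | 77.8% |
| 5% | 8% | 0.034 | 79.1% |
| 20% | 5% | 0.044 | 79.6% |
| 20% | 8% | 0.113 | 82.4% |
| 30% | 8% | 0.148 | 83.9% |

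Oedema therefore adds little unless it is both common and marked. The documents do not settle its prevalence. Section 2.2 requires low WHZ or low MUAC of every child, which suggests few children with oedema. Section 2.5 lists bilateral oedema as an admission criterion of its own. The last line of section 3.5 can be read as admitting only children with oedema, which contradicts section 2.2; these passages must be reconciled.

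**Analysis without oedematous children**, with SD = 1.7 × √(1 − R²): at 5% prevalence, 256 per arm and half-width 0.290-0.295; at 30%, 189 per arm and 0.317-0.342.

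**Simulation check**, 6,000 trials per setting, five terms, true difference 0.40. With 20% prevalence, 5% fluid and a further R² of 0.05, the mean estimate was 0.400 in both models. Half-width was 0.287 unadjusted and 0.275 adjusted; power was 78.3% and 81.5%. With 5% prevalence, 2% fluid and nothing else explained, the mean estimate was 0.398 in both, and power was 77.4% and 77.1%.

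**The case against.** A pre-specified unadjusted comparison in a 1:1 trial is a legitimate choice. The benefit rests on an R² that nothing in the documents supports. The outcome is already a change per kilogram, and eligibility truncates WHZ and MUAC, so they may explain little. At R² = 0.02 power would be 78.3% against 77.9%. The secondary outcomes corrected for baseline are mostly levels, for which adjusting for the outcome's own baseline is standard, so the contrast with the primary outcome is not a clear inconsistency. The primary model is already fixed, so baseline tests do not by themselves open it to choice.

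On oedema, fluid loss occurs in both arms and cancels in expectation. One SD of chance imbalance, d × √[p(1 − p) × 2/270], moves the estimate by 0.007-0.027 at 5% prevalence and by 0.056 at 30% with 8% fluid, against a half-width of 0.287. Changing the primary model is also risky where investigators are unblinded to the bottles (section 4.1) and weight gain goes into reports to the monitoring committee (section 6.3, arm not stated).

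Most of this stands as a limit on size. It does not remove the point: the downside is about 0.4 of a power point, the break-even is low, and the data are in hand. Cancellation of fluid loss assumes that oedema clears alike in both arms; the sensitivity analysis examines that assumption. The timing risk is real, and the fix depends on it.

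**Conclusion.** The point holds. The primary model has only the arm term, and no analysis of weight gain uses oedema status. The unadjusted estimate remains valid, so the loss is in precision and interpretation, not in bias.

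For the five-term model, the effect runs from a loss of 0.4 power point if the covariates explain nothing to gains of 1.7, 3.8 and 8.0 points at R² of 0.05, 0.10 and 0.20. The half-width goes from 0.287 to between 0.289 and 0.258. A gain is likely but not certain: R², oedema prevalence and fluid fraction are all assumptions. The analysis without oedematous children is less precise than the primary one and can serve only as a consistency check. The change is worth making because it is nearly free.

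**What to change.** In a dated SAP amendment, made before any outcome data by arm are seen:

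1. Make the primary model a linear regression of weight gain on arm plus baseline oedema (none, +, ++), WHZ, MUAC and age. Keep the unadjusted model as a sensitivity analysis. Local government area is optional, since section 2.3 describes no stratification.
2. State the form of the continuous terms, how a missing baseline value is handled, and whether + and ++ are merged if ++ is rare.
3. State what had been seen by arm, and by whom, at the date of the amendment. If the timing cannot be documented, keep the unadjusted model as primary and name this adjusted model as the single supportive analysis.
4. In either case, add one sensitivity analysis of the primary outcome in children without oedema at baseline, reported as an estimate with its interval and read for consistency, not significance.

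Baseline WHZ includes any oedema fluid. That does not bias the arm effect, because WHZ is measured before randomisation, but the covariate coefficients should not be interpreted. Gain should not be re-based on the first oedema-free weight: that base is post-randomisation and undefined for children whose oedema never clears.

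The cost is SAP wording, with no new data or visits. If the covariates explain nothing, power falls by about 0.4 point (0.5 with local government area).
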